8.6.2 Participants removal

Request by the participant to withdraw from the study at any time:

- Participant does not wish to continue in the study for personal reasons (or even without reason);
- Participant does not wish to continue in the study due to AEs of the investigational drugs (undesirable effects possibly related to the investigational drugs);
- Participant does not wish to continue for reasons other than AEs, for example, unavailability, intolerance to study procedures, or even personal will.

The researcher may withdraw the participant from the study for one of the following reasons:

- Positive response to reevaluation of any of the exclusion criteria, from admission to the first treatment period or on a subsequent occasion;
- Non-adherence to the protocol requirements;
- AEs, symptoms, or signs of possible toxicity;
- Intercurrent illness requiring medication;
- Any other condition that, in the researcher's judgment, is in the participant's best interest for maintaining health.

The details and reasons for the participant's withdrawal from the study will be recorded in the CRF and must be reported to the sponsor.

8.6.3 Criteria for participants discontinuation

In order to ensure the well-being of the participants, the study may be interrupted if, at the discretion of the Principal Investigator, or the Sponsor, it is established that the risks to which the participants are being subjected to, are greater than initially anticipated, or even at any time by the participant's own decision.

Subjects may have their participation in the study prematurely terminated based on the withdrawal criteria described above.

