3. STUDY PLAN

3.1 General study design

Open-label study, conducted at a single center, with the aim of being the first human trial with the new BZ371A formulation in order to guide future clinical studies such as to understand safety, tolerability, and systemic bioavailability of the peptide topically applied.

The study will comprise only one group, consisting of 6 men and 6 women.

The formulation will be administered in a single dose, topically, followed by medical and laboratory analyses for safety assessment, and blood collections for pharmacokinetic analysis.

The concentration of BZ371A and its fragments in the blood will be measured by an appropriate analytical method, developed for this purpose and previously validated. The collected blood will be

analyzed by the company *Unidade Integrada de Farmacologia e Gastroenterologia* (UNIFAG), the same company that validated the analytical method, and will not be stored or used for any other purpose.

The visits and procedures are illustrated in the table below:

CHART 1. VISITS AND BZ371CLI003 STUDY PROCEDURES

| Visit | V-1 | V0 | V1 |
|--|-----------|-----------------------|-----------------|
| Day | D-1 | D0 | D7 |
| Interval | -7 a 0 | 0 | +2 a -2 |
| Visit Name | Screening | PK | Safety revision |
| ICF | X | | |
| Demographic data | X | | |
| Medical history | X | X | |
| Physical exam | X | | X |
| Genitalia exam | X | X / X ^(*) | X |
| Anthropometric data | X | | |
| Vital Signs | X | X / X ^(**) | X |
| Concomitant medication | X | X | X |
| Blood collection for laboratory analysis | X | X ^(*) | |
| Urine collection | X | X ^(*) | |
| Electrocardiogram | X | X ^(*) | X |
| Eligibility | X | X | |
| Blood sample collection for PK | | X | |
| BZ371A application | | X | |
| AE collection | | X | X |
| Next visit scheduling | X | X | |
| Study dismissal | | | X |

^{*}: after 360 minutes after IP application

^{**}: after IP application at 30, 60, 180 and 360

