5.2 Safety analysis and tolerability procedures

5.2.1 *Clinical and physical evaluation*

Demographic data, medical history, current medication, and adverse events will be collected through direct interviews with the research participant and/or their family members when necessary. The use of any concomitant medication should be recorded, including its indication.

5.2.2 *Vital signs and anthropometric*

The collection of vital signs aims to detect the presence of any AE, especially hypotension. In order to evaluate safety, the following parameters should be collected and recorded: systolic blood pressure (SBP), diastolic blood pressure (DBP), heart rate (HR), respiratory rate (RR) and axillary temperature (T°C).

Before evaluation period, participants should remain at rest (sitting and without physical effort) for at least 5 minutes in a room at room temperature. Blood pressure measurement should be obtained in only one of the participant's arms (right or left), which should be selected as a reference for subsequent measurements. The examiner should perform three measures with an interval of one minute between them; the first measurement should be discarded and the real blood pressure that should be considered is the average between the last two measurements.

The normal values are: SBP between 90-140 mmHg and DBP between 60-90 mmHg. Values outside these ranges will be considered as medical history or AE (whether before or after IP administration) and should be reported as such if there is clinical significance in the physician's opinion.

Vital signs should be collected at V-1, V0, and V1. At V0, they will be collected before IP administration (concomitant with medical evaluation); and in 30, 60, 180, and 360 minutes after IP administration.

Arterial hypotension should be recorded as an AE. Its occurrence should be associated with the following values: 20 mmHg reduction in SBP, 10 mmHg reduction in DBP, and/or 20% increase in HR. These values should all be related to the data recorded on the same day, before IP administration.

Weight, height, and body mass index (BMI) will be measured only at V-1 for eligibility and characterization of the evaluated sample.

5.2.3 *Physical and genitalia exam*

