In order to be completed, physical examination must be performed at V-1 and V1 to capture diseases and AEs, respectively. The assessment includes a general inspection (skin, oropharynx, and appendages), and cardiovascular, pulmonary, digestive, musculoskeletal, peripheral, and neurological exams.

Physical examination of the male or female genitalia must be performed at all visits: at V-1, for eligibility assessment; at V0, before and 360 minutes after IP administration, for AE assessment; and at V1, for AE assessment.

5.2.4 *Blood and urine sample collection*

In order to evaluate the systemic safety of the PSI, blood and urine will be collected before (at V-1) and after the application of the IP (at V0 at the 360-minute time point), for analysis of the following laboratory tests: (i) complete blood count, including platelets; (ii) coagulogram, including PT and PTT; (iii) biochemistry, including glucose, sodium, potassium, urea, creatinine, chloride, total calcium, phosphorus, total and fractionated proteins (albumin and globulin), TGO, or AST, TGP or ALT, alkaline phosphatase, gamma GT, total cholesterol, HDL cholesterol, triglycerides, pH; (iv) urinalysis.

In addition, blood will be collected from women during the V-1 visit for the β -HCG test and confirmation of absence of pregnancy, allowing the participant to be included in the study.

Approximately 20 ml of blood will be collected per evaluation (V-1 and V0), totaling 40 ml of blood for laboratory tests.

Any difference between the baseline and post-application of the IP should be evaluated by the examiner and, if clinically significant, should be noted as an AE.

5.2.5 *Electrocardiogram*

In order to evaluate the cardiac safety of PSI, an ECG examination will be performed at all visits. At V0, it should be performed 360 minutes after the administration of PSI, with a window of +/- 30 minutes. At V-1 and V1, the cardiac evaluation can be performed concurrently with the clinical evaluation.

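### No dosing interval or between-participant review is stated, so all 12 doses could precede the first 360-minute safety results; dosing a pair first would cap this at 2

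*Combined protocol and SAP*

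**What the plan says.** Section 3.1 describes an open-label, single-centre study "with the aim of being the first human trial with the new BZ371A formulation". On group and dose it reads: "The study will comprise only one group, consisting of 6 men and 6 women", and "The formulation will be administered in a single dose, topically, followed by medical and laboratory analyses for safety assessment". A participant's dosing visit is tied only to that participant's own screening visit, which must be no more than a week earlier. Sections 3.1, 4.2, 5, 6.5, 8.6 and 9 contain nothing that links one participant's dosing to another's results.

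Post-dose safety data on the dosing day arrive in this order:

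- Skin irritation and sensitivity are observed from application (6.5), and AEs are collected at the visit (Chart 1).
- Vital signs are taken before application "and in 30, 60, 180, and 360 minutes after IP administration" (5.2.2).
- The genital examination is scheduled "at V0, before and 360 minutes after IP administration, for AE assessment" (5.2.3).
- Blood and urine for safety tests are collected at screening and "after the application of the IP (at V0 at the 360-minute time point") (5.2.4).
- For the ECG, "it should be performed 360 minutes after the administration of PSI", with a window of 30 minutes either way (5.2.5).

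On stopping, 8.6.3 says "the study may be interrupted if, at the discretion of the Principal Investigator, or the Sponsor", the risks are found to exceed what was foreseen. Section 8.6.1 lets the sponsor suspend at any time. Section 7.1 says safety is evaluated throughout the study. None of the three names a point at which data are reviewed before further dosing.

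**The concern.** In a single-dose study, the power to interrupt has preventive value only while someone remains undosed. Safety is a primary goal (2.1), the participants are healthy and expect no individual benefit (8.5.1), and the study has one dose level with no lower step. That level was set from the highest workable concentration in the gel, with supporting in vivo data (6.1). Absence of systemic exposure in humans is something the study sets out to confirm (1.1), so it cannot be taken as given.

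Some possible effects cannot be detected before 360 minutes under this schedule. Table 1 lists tubulopathy, and Chart 4 monitors it only by biochemistry and urinalysis. The first post-dose ECG, which Chart 4 names for arrhythmia caused by hypotension, comes at about the same time. If all 12 participants are dosed on one morning, such a finding in the first participant cannot spare any of the other 11.

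**Working it through.** The plan gives no figure for dosing spacing, so there is none to reproduce. The inputs are N = 12 (3.1), one dose each (3.1), and assessment times of 30 and 360 minutes (5.2).

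**Step 1: the spacing at which all 12 are dosed first.** Twelve doses have 11 gaps. With equal spacing s, the last dose falls before the first participant's reading at time t if 11s < t, that is s < t/11.

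- 30-minute vital signs: 30/11 = 2.7 minutes.
- 360-minute assessments: 360/11 = 32.7 minutes.
- Earliest ECG within its window: 360 − 30 = 330 minutes, and 330/11 = 30.0 minutes. Between 30.0 and 32.7 minutes, an early ECG could just precede the last dose.

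**Step 2: how many are dosed before each reading.** The number dosed before time t is the smaller of 12 and t/s rounded up.

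| Spacing (min) | Dosed before first 30-min vital signs | Dosed before first 360-min assessments | Undosed at 360 min |
|---|---|---|---|
| 0 | 12 | 12 | 0 |
| 10 | 3 | 12 | 0 |
| 30 | 1 | 12 | 0 |
| 60 | 1 | 6 | 6 |
| 360 or more | 1 | 1 | 11 |

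The text allows every row, so exposure before the first 360-minute assessments is anywhere from 1 to 12. At 10-minute spacing, a hypotension signal at the first 30-minute reading could still spare 12 − 3 = 9 people. A laboratory signal could spare none.

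**Step 3: laboratory turnaround.** The 32.7-minute figure is for sample collection; results come later. No turnaround is stated. If it is T minutes, the limit becomes (360 + T)/11. For an assumed 1 day, (360 + 1440)/11 = 163.6 minutes; for 2 days, (360 + 2880)/11 = 294.5 minutes. For laboratory findings, 32.7 minutes is therefore the most lenient case.

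**Step 4: what a first-dosed pair would detect.** The documents give no event rates, so p is assumed. The chance that at least one of two participants shows the effect is 1 − (1 − p)²:

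- p = 10%: 1 − 0.81 = 19%
- p = 25%: 1 − 0.5625 = 44%
- p = 50%: 1 − 0.25 = 75%

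For an effect in one sex only, the pair holds one person at risk and the chance is p itself: 10%, 25%, 50%.

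**Step 5: what a clean pair rules out.** With 0 of 2 affected, the one-sided 95% upper limit for the risk is 1 − 0.05^(1/2) = 78%. A clean pair is a check for common effects, not evidence that the dose is safe.

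**The case against.** A reader might infer that 8.6.3 can protect nobody until the 360-minute results are in. The documents do not support that. The section does not restrict which data may be used, and the Principal Investigator can act alone. Vital signs come at 30, 60 and 180 minutes, skin is watched from application, and AEs can be reported at any time. All 12 doses precede the first vital signs only if spacing is under 2.7 minutes.

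Most of the risks in Table 1 can appear through these earlier routes: local reactions, headache, hypotension and diarrhea. Chart 4 assigns priapism to the genital examination, but a participant can report it sooner. This part of the objection stands, and it narrows the point to effects first seen at 360 minutes.

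A reader might also infer that slow reporting of non-serious AEs to the sponsor disables the safeguard. It does not, because the investigator is on site and need not wait for the sponsor.

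The context also lowers the stakes. The study gives one topical dose. Preclinical topical use showed no systemic bioavailability or hypotension (1.1), and tubulopathy was seen only in rats at high systemic doses (7.2). The earlier exploratory human studies reported one mild, self-resolving case of pruritus (7.2). The site may space doses under its own procedures, and nothing in the documents shows that it plans to dose everyone together. These points moderate the risk, but they do not supply a review point.

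Finally, a pair detects little: it misses an effect with a 10% risk 81% of the time, and a fully sequential schedule would expose only 1 before the first results. Both points are true. The fix offers a guaranteed ceiling in place of an unstated number.

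**Conclusion.** The gap is real but limited. The protocol permits all 12 doses before any 360-minute laboratory, urine, ECG or scheduled genital examination result, if spacing is under about 33 minutes. An interruption would then come too late to prevent exposure to effects first visible in those assessments, chiefly renal, other laboratory and ECG changes. It would not be too late for effects that show in earlier vital signs, on the skin or as reported AEs, provided some participants are still undosed.

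The size is 1 to 12 exposed before the first 360-minute assessments, depending on a schedule the protocol does not state. With a first-dosed pair, 2 are exposed before the first review. The spacing limit assumes equal gaps; the detection chances assume independent participants and assumed risks. This is a modest improvement to the design, not an error in a stated figure, and it is worth making because it costs little.

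**What to change.** In 3.1, add: *One man and one woman are dosed first. The other 10 participants are dosed only after the investigator has reviewed the pair's AEs, vital signs, genital examination, ECG and 360-minute laboratory results, and the sponsor has agreed.* In 8.6.3, refer to this review as a point at which interruption is considered. Including both sexes matters because at least one listed risk, priapism, applies to men only.

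The cost is about 1 to 2 days' delay, on an assumed laboratory turnaround. Because dosing must follow screening within 7 days, the other 10 should be screened with that delay in mind. If the protocol is already approved, this changes the study plan and needs an amendment under 8.7.1, with ethics committee and sponsor approval. Sample size, PK sampling times and endpoints do not change.

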8.7 Criterions for change in the approved Protocol

8.7.1 Amendments

Defined as changes that alter the potential safety risk to the participants and/or the study plan, such as changes in dosage regimen, alteration of the number of participants, or additional blood samples to be collected. Amendments can occur before and/or after the study commencement.

Any change to the study plan requires an amendment to the protocol. The Investigator must not make any changes to the study without the approval of the Ethics Committee (EC) and the Sponsor, except when necessary to eliminate immediate obvious risks to the participants. An amendment to the protocol aimed at eliminating an immediate obvious risk to the participants can be promptly implemented, but the change must then be documented in an amendment, notified to the EC within 5 business days, and submitted to the appropriate regulatory agency within the required timeframe. All protocol amendments must be reviewed and approved following the same process as the original protocol.

8.7.2 *Corrections*

Defined as changes before the study commencement that do not alter the potential safety risk to the participants and/or the study plan.

Any necessary corrections to this protocol after its initial version approved by the Ethics Committee (EC) should be made with the approval of the sponsor.

8.8 Protocol deviations and violations

The procedures described in the protocol must be followed in full, taking appropriate measures to prevent protocol deviations. However, in the event of any complications, it is the responsibility of the researchers to analyze and evaluate the situation, as well as take appropriate actions accordingly.

Protocol deviation is defined as any failure to comply with the procedures or requirements defined in the version of the protocol approved by the Ethics Committee (EC) without significant implications for the study integrity, data quality, or participant rights and safety. On the other hand, protocol violation refers to a deviation from the protocol that may affect data quality, compromise the integrity of the study, or impact the safety or rights of the participants. In general, a significant deviation from the protocol is considered a protocol violation, while a minor deviation is considered a protocol deviation.

Any deviation from the plan outlined in this protocol must be described, justified, and included in the Final Report.

9. STATISTICAL ANALYSIS PLAN

The statistical analyses will aim to describe the pharmacokinetic parameters. Adverse events (AEs) will be analyzed qualitatively. Therefore, every detected adverse event will be described in the results, characterized by: (i) identification, if possible, as a medical entity (sign, symptom, or disease); (ii) intensity (mild, moderate, or severe); (iii) severity, whether it is a serious adverse event (resulting in death, abortion, immediate risk of death, hospitalization or prolongation of hospitalization, or disability); (iv)

duration; (v) resolution (complete, partial, or unresolved); (vi) mode of resolution (spontaneous or requiring medicinal treatment); and (vii) causality with the investigational product (IP).

Participants in whom the IP has been administered will be included in the analysis.

A sample size of 12 participants is considered adequate for a pharmacokinetic curve.

10. DATA QUALITY CONTROL MANAGEMENT

The quality of the conducted clinical study will be ensured in accordance with the Standard Operating Procedures (SOPs) of the Research Center, which comply with regulatory requirements of the ICH (International Council for Harmonization), Good Clinical Practice (GCP) guidelines, and current national regulations. The study data management will be conducted in accordance with the applicable regulations.

10.1 Source document

The source documents are all original documents in which the first record of collected data was made, including but not limited to:

- Medical records;
- Informed consent forms;
- Questionnaires;
- Dispensation control records and accounting of investigational product.

The completion of source documents is the responsibility of the principal investigator and should be performed by either the principal investigator or a designated member of their team. Availability of the source documents for verification, by the sponsor's assigned monitor during monitoring visits, is mandatory.

All documents related to the clinical study, including but not limited to source documents and the physical study file, should be archived under the responsibility of the Research Center for a period of 10 years from the close-out visit of the clinical study. These documents are subject to auditing by the sponsor as well as regulatory authorities at any time within the aforementioned period. In the case archiving outside the Research Center, the storage location must be informed to the sponsor at the time of close-out through a formal declaration.

10.2 Data acquisition - Clinical file

The raw data generated during the conduct of the study will be directly recorded in the study's paper Case Report Form (CRF). All data related to the study will be the responsibility of the Principal Investigator until its archiving.

Clinical data will be collected by the investigator or delegated responsible party(ies), and the CRF should document each phase throughout the clinical study. All screened research participants will be recorded in the CRF, regardless of their randomization to the clinical protocol, ensuring traceability of the records for participants considered as selection failures.

10.3 Data validation

Data verification will be carried out by the data management department, based on cross-checking between different fields of the CRF. The development of this process takes into account each field of the CRF and the cross-referencing of fields within the same visit and between visits, allowing for verification of all fields considered essential for statistical analysis and obtaining study results. This verification aims to ensure the quality of the collected data.

10.4 Audit

During the study or after its completion, the conduct of the study and/or relevant documentation may be audited by the Sponsor or Regulatory Agencies through an independent visit, or by the Research Center through routine quality control audits. These audits aim to assess the conduct of the clinical study and compliance with the clinical protocol, SOPs, GCPs, and applicable regulatory requirements.

